Appendix II details the conventions for presentation of data in outputs.

The mock up templates provided with this SAP describe the presentations for this study and therefore the format and content of the summary tables, figures, and listings to be provided by Clinipace Clinical Research Biostatistics.

5.2 Missing data

Generally, the last-observation-carried-forward procedure will be used to estimate the missing data for efficacy variables.

Note that a subject must report at least 4 values for a week in order for the weekly mean of the 24 hour Worst Itching Intensity NRS to be non-missing.

No imputation will be done for estimating the missing values for safety variables and time to event data.

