10.7 Efficacy Analysis

The efficacy of LT5001 drug product will be assessed via the following:

Part A:

- Change in mean Worst Itching Intensity using NRS.
- Proportion of patients reduced NRS from baseline with respect to weekly mean of the daily 24-hour Worst Itching Intensity NRS score from baseline to the end of Week 4.
- Change from baseline in 5-D Itch Scale score at the end of Week 4.

CONFIDENTIAL

- Change from baseline in total Skindex-10 Scale score at the end of Week 4.

Part B:

- Change in mean Worst Itching Intensity using NRS.
- Proportion of patients reduced NRS from baseline with respect to the weekly mean of the daily 24-hour Worst Itching Intensity NRS score from baseline to the end of Week 8.
- Change from baseline in 5-D Itch Scale score at the end of Week 8.
- Change from baseline in total Skindex-10 score at the end of Week 8.

Mixed-effect model repeated measures analysis of covariance will be applied to compare the treatment groups for efficacy endpoints (i.e. change of NRS, change from baseline in 5-D Itch Scale, change from baseline in total Skindex-10), with baseline itch and prior anti-itch medication use as covariates, and patient as a random effect.

Proportion of patients improved NRS from baseline (2-points, 3-points, or 4-points) was evaluated at each time point compared between treatment group using logistic regression analysis.

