The FAS will be used for efficacy endpoint evaluation. Efficacy analysis will be repeated on the PP Population.

The following efficacy endpoints will be assessed by Part of study.

Part A:

- Change in mean Worst Itching Intensity using NRS from baseline to the end of Week 4.
- Proportion of patients reduced NRS from baseline with respect to weekly mean of the daily 24-hour Worst Itching Intensity NRS score from baseline to the end of Week 4.
- Change from baseline in 5-D Itch Scale score at the end of Week 4.
- Change from baseline in total Skindex-10 Scale score at the end of Week 4.

Part B:

- Change from baseline to the end of Week 8 in mean Worst Itching Intensity using NRS (Primary endpoint in Part B)
- Proportion of patients reduced NRS from baseline with respect to the weekly mean of the daily 24-hour Worst Itching Intensity NRS score from baseline to the end of Week 8.
- Change from baseline in 5-D Itch Scale score at the end of Week 8.
- Change from baseline in total Skindex-10 score at the end of Week 8.

The efficacy analysis will be based on a linear mixed effect model for repeated measurements (MMRM) using all the longitudinal observations at each post-baseline visit through the last visit.

To select an appropriate covariance model, covariates of baseline itch and status of prior anti-itch medication use

Proportion of patients improved NRS from baseline (2-points, 3-points, or 4-points) was evaluated at each time point compared between treatment group using logistic regression analysis.

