10.1 Primary efficacy analysis

Numerical Rating Scale (NRS)

Numerical Rating Scale (NRS), an unidimensional scale, which may be the most widely used is a validated measurement of UP intensity in HD patients. Patients can be asked to rate their itch intensity from 0 (“no itch”) to 10 (“worst imaginable itch”) with the NRS.

Patients will be recorded the daily Worst Itching Intensity in the patient diary and review will be conducted in each visit.

QMS Document Name: Statistical Analysis Plan	Page 17 of 33
QMS No (include version ref): STF-015-GL.02	Document date: 09JUL2019
CONFIDENTIAL	

The weekly mean of the 24-hour Worst Itching Intensity NRS score will be defined as the sum of the daily Worst Itching Intensity NRS scores reported during a specific week during the Treatment Period (e.g., Days 1 to 7, Days 8 to 14, Days 15 to 21) divided by the number of days with non-missing scores for that week. If the daily worst itching score is missing for >3 days during a specific week, the corresponding weekly mean worst itching score will be set to missing. Additionally, subjects who discontinue treatment but continue on study and report NRS scores will have their NRS scores censored following discontinuation of treatment; missing data rules will apply to these censored values as though they had missing values/ dropped out from the study entirely.

The baseline score was defined as the average of the daily 24-hour Worst Itching Intensity NRS scores reported over the 7-day Run-in Period. As defined in the protocol, to be randomized, subjects had to report at least 6 non-missing Worst Itching Intensity scores from the start of the 7-day Run-in Period and mean NRS score >4 to qualify.

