As a continuous variable, the data value of NRS on the each visit will be derived based on the average value of the values that each subjects had recorded from the previous visit day to next visit day. Change from baseline in NRS will be summarized as descriptive statistics by overall subjects and treatment group for Part A and Part B. For Part B, it will further be analyzed using mixed-effect model repeated measure analysis of covariance to compare the treatment group considering covariates (baseline itch and prior anti-itch medication use). Additionally, treatment group, time, an interaction term for treatment group and time will be included into the model as factors. The model will be used to estimate the NRS at end of treatment. Least square means and their standard errors, along with their 95% confidence interval (CI) of treatment difference will be calculated.

To perform MMRM, SAS programming will be used as follows.

```
proc mixed data= dataset ;
  class treatment time subject prior_med;
  model NRS=treatment time treatment*time baseline_itch prior_med /solution ddfm=kr;
  lsmeans treatment*time/cl pdiff;
  repeated time/type=un subject=subject;
run;
```

By using derived NRS at the timepoint, the subjects reduced NRS from baseline (≥ 2 -points, ≥ 3 -points, ≥ 4 -points) to each time point will be categorized. It will be summarized by frequency and percentage of subjects. For Part A and B, logistic regression analysis will be further performed to compare treatment group differences at each time-point, providing with odds ratio and 95% CI.

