10.2 Secondary efficacy analyses

In Part A, the secondary efficacy endpoints will be summarized using descriptive statistics. Statistical comparisons will only be performed in park B using a two-sided test at a significance level of 5%, and 95% CI and a P-value will be reported in case of efficacy analysis.

5-D Itch Scale

The 5-D itch scale was developed as a brief but multidimensional questionnaire designed to be useful as an outcome measure in clinical trials. The five dimensions are degree, duration, direction,

QMS Document Name: Statistical Analysis Plan	Page 18 of 33
QMS No (include version ref): STF-015-GL.02	Document date: 09JUL2019
CONFIDENTIAL	

disability and distribution. The duration, degree and direction domains each included one item, while the disability domain had four items. All items of the first four domains were measured on a five-point Likert scale.

The five-point Likert scale are rated from 1 to 5 points. For disability domain, the highest score on any of the four items will be used. For the distribution domain, the number of affected body parts is tallied (potential sum 0–16) and the sum is sorted into five scoring bins: sum of 0–2 = score of 1, sum of 3–5 = score of 2, sum of 6–10 = score of 3, sum of 11–13 = score of 4, and sum of 14–16 = score of 5. The total score of 5-D itch will be the sum of the 5 domains, ranging from 5 to 25 points.

5-D itch scale will be assessed at Visit 1, Visit 5, Visit 7 in Part A and Visit 1, Visit 3, Visit 5, Visit 7, Visit 9 (End of study) in Part B. Baseline of 5D itch score will be assessed at Visit 1.

Change from baseline in 5-D Itch Scale score at week 4 in Part A and Week 8 in Part B (total score and score for each domain) will be summarized by treatment group and visit.

In Part A and B, mixed-effect model repeated measure analysis of covariance will be performed to compare the treatment group considering covariates (baseline itch and prior anti-itch medication use).

Skindex-10 scale

Skindex-10 consists of 10 questions used to evaluate how the patient's itch affects three important domains of quality of life.

The total score of skindex-10 scale is the sum of the numeric value of each answered question. The domain scores are sums of the following: disease domain (questions 1 to 3), mood/emotional distress domain (question 4 to 6), and social functioning domain (questions 7 to 10)

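### LOCF is the written general rule for missing efficacy data and nothing exempts the Part B primary MMRM, so carried-forward scores may enter the Week 8 contrast

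*SAP*

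**What the plan says.** On missing efficacy data, SAP 5.2 reads: "Generally, the last-observation-carried-forward procedure will be used to estimate the missing data for efficacy variables". Protocol 10.9 has the same sentence. Both add a rule for other kinds of data: "No imputation will be done for estimating the missing values for safety variables and time to event data".

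On the model, Protocol 10.7 says: "Mixed-effect model repeated measures analysis of covariance will be applied to compare the treatment groups for efficacy endpoints", and names change in NRS, 5-D Itch and Skindex-10. SAP Section 10 (Efficacy) describes a "linear mixed effect model for repeated measurements (MMRM) using all the longitudinal observations at each post-baseline visit through the last visit". SAP 10.1 adds: "The model will be used to estimate the NRS at end of treatment". Its PROC MIXED code uses an unstructured covariance and reads a generically named dataset. SAP 10.2 applies the same kind of model to the 5-D Itch Scale ("In Part A and B, mixed-effect model repeated measure analysis of covariance will be performed to compare the treatment group considering covariates") and to Skindex-10.

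On when an NRS value is missing, SAP 5.2 and 10.1 require at least four daily scores for a weekly mean. SAP 10.1 also says that patients who stop treatment but stay on study "will have their NRS scores censored following discontinuation of treatment; missing data rules will apply to these censored values". Later in 10.1, the value at each visit is described as "the average value of the values that each subjects had recorded from the previous visit day to next visit day", with no minimum number of scores.

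**The concern.** The general rule covers every efficacy variable, and the Part B primary endpoint is one. A programmer who follows SAP 5.2 literally would fill missing weekly means with the last observed one and then fit the MMRM. A programmer who follows SAP Section 10 and common practice would fit the model to observed values only. The code runs unchanged on either dataset, so it does not settle the matter.

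The choice matters because an MMRM estimates the Week 8 mean from incomplete records under a missing-at-random assumption. Carrying a score forward instead treats an earlier value as if it had been measured at Week 8. If scores are still falling, a patient who left in Week 3 is recorded as having stopped improving. The Week 8 contrast then depends on how many patients leave each arm and when. A choice between the two results made after unblinding would not be credible.

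**Working it through.** **The text.** For an efficacy value that is missing, SAP 5.2 and Protocol 10.9 prescribe LOCF, softened by the word *generally*. No exception is written for endpoints analysed by MMRM. SAP Section 10 points to observed data without saying that only observed values are used. The reference to missing-data rules in SAP 10.1 may mean only the rule that blanks a week with more than three missing days. Even so, LOCF is the only rule in either document for replacing a missing efficacy value.

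**Inputs for the size.** The plan has no figure to reproduce: Protocol 10.1 and SAP 3.2 say that no formal sample size calculation was done. Everything below is assumed.

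- cP and cA: mean Week 8 change on placebo and active, -1.0 and -2.5, so the true effect is -1.5.
- pP and pA: dropout in each arm, non-informative, with last observed week k equally likely to be 1 to 7.
- f: mean share of the Week 8 change that a dropout has not yet shown.

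**Formula.** Under LOCF the arm mean is c × (1 − f × p). The contrast, active minus placebo, is therefore (cA − cP) + f × (pP × cP − pA × cA). The second term is the bias.

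**Value of f.**

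- Linear over 8 weeks: mean of (8 − k)/8 for k = 1 to 7 = (28/8)/7 = 0.50.
- Linear to a plateau at Week 4: (0.75 + 0.50 + 0.25 + 0 + 0 + 0 + 0)/7 = 0.21.
- Exponential approach with a 2-week time constant: about 0.20.

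**Results with f = 0.50.**

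| Dropout placebo/active | Bias | LOCF contrast (true -1.5) |
|---|---|---|
| 5/5% | 0.5 × (-0.05 + 0.125) = +0.04 | -1.46 |
| 10/10% | 0.5 × (-0.10 + 0.25) = +0.075 | -1.43 |
| 20/20% | 0.5 × (-0.20 + 0.50) = +0.15 | -1.35 |
| 10/20% | 0.5 × (-0.10 + 0.50) = +0.20 | -1.30 |

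With f of 0.20 to 0.21, the 5/5% and 10/20% biases fall to about +0.02 and +0.08.

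**No true effect (both arms -1.0, f = 0.50).** Equal dropout gives 0. Dropout of 10/20% gives 0.5 × (-0.10 + 0.20) = +0.05, against the drug. Dropout of 20/10% gives -0.05, in its favour.

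**Simulation check.** Further assumptions: 30 per arm, baseline mean 6.5 restricted to above 4, SD 2.0, correlation 0.6, scores bounded to 0–10, and a t reference in place of Kenward-Roger. The SAP 10.1 model was fitted after LOCF and to observed data.

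- Linear, 5/5%: -1.43 after LOCF, -1.47 observed. The two disagree on p < 0.05 in 4% of trials.
- Linear, 10/20%: -1.28 after LOCF, -1.49 observed. Power is 82% against 91%, and the two disagree in 10% of trials.
- Linear, 10/20%, no effect: type I error 6% under both.
- Exponential, 10/20%: -1.37 after LOCF, -1.45 observed, with no loss of power.

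The protocol plans 45 per arm where the SAP plans 30. At 45 per arm the linear 10/20% case gives -1.29 against -1.49.

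**The case against.** The strongest reply is that the model-specific text governs. MMRM is normally fitted to observed data, SAP Section 10 speaks of all the longitudinal observations, SAP 10.1 averages values that patients recorded, and the unstructured model handles incomplete records. The word *generally* leaves room for this, and LOCF has another natural use in the logistic regressions at each time point. This makes an observed-data fit the more likely intention. It does not make it the written rule.

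A reader might infer the stronger claim that the plan puts carried-forward scores into the MMRM. The documents do not support that: they permit it and do not state it. Nor does the sentence on safety and time-to-event data prove that the MMRM endpoints are caught. It is a rule for other data, and its silence on the MMRM shows little.

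Three further points stand in part.

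- The per-protocol repeat (SAP Sections 4 and 10) requires completed study procedures and weekly means for at least 75% of weeks, so it excludes most dropouts. It limits the harm but does not define the primary analysis.
- The two descriptions of the NRS input nearly coincide in Part B, where visits are weekly (Protocol synopsis, Study Design), and SAP 5.2 repeats the four-score minimum. That conflict is minor.
- Early leavers are due end-of-study procedures at or within 7 days of discontinuation (Protocol 5.1.3), so less may be missing for 5-D Itch and Skindex-10.

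The rules on denominators for missing observations in SAP 5.1 and Appendix II concern presentation and do not settle the model input.

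**Conclusion.** The point holds as an unresolved rule for the primary analysis and should be fixed. The general LOCF rule is explicit, no exemption for the MMRM endpoints is written, and the same data can give two Week 8 results.

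If LOCF is applied, bias arises when scores are still changing and there is a true effect or unequal dropout. With equal dropout it pulls the effect towards zero. With unequal dropout it can go either way or cancel. A reader might infer that LOCF would favour the drug or seriously inflate the false-positive rate. Nothing in the documents supports that, and in the moderate case examined type I error was the same under both methods.

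In the illustration the shift is about 0.04 to 0.20 NRS points on a true effect of -1.5 with a linear course, and about 40% of that if change levels off early. These figures rest on assumed changes, dropout and timing. Confidence is high that the ambiguity exists and much lower about its size in this trial.

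**What to change.** Before unblinding, state in SAP 5.2 and 10.1 that the MMRMs for NRS, 5-D Itch and Skindex-10 are fitted to observed values with no prior imputation, and that LOCF is a sensitivity analysis only. Name the weekly means in SAP 10.1, with at least four daily scores, as the NRS input, and align the later between-visit wording with them.

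Record the change in SAP 2.1, which now reports no difference from the protocol, as a departure from Protocol 10.9. Alternatively, align Protocol 10.9 at the next amendment.

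No new data are needed. The cost is a few sentences and one extra sensitivity run. The standard error changes slightly and in either direction: in the simulation with 30 per arm and 20/20% dropout it was 0.45 observed against 0.43 under LOCF with a placebo change of -1.0, and 0.44 against 0.45 with a placebo change of -2.5. Editing the protocol text may also require the agreement and ethics steps in Protocol 12.2 and 13.1.2.

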5.3 Observation and analysis times

Reference Start Date and Study Day

Reference start date is defined as the day of randomization and study day relative to the reference start date will appear in every listing where an assessment date or event date appears.

Study day will be calculated from the reference start date and will be used to show start/stop day of the assessments and events relative to the first administration of study treatment.

- If the date of the event is on or after the reference date, then:

$$\text{Study day} = (\text{date of event} - \text{reference date}) + 1.$$
- If the date of the event is prior to the reference date, then:

$$\text{Study day} = (\text{date of event} - \text{reference date}).$$

In case of that event date is partial or missing, the date will appear partial or missing in the listings, and Study Day, and any corresponding durations will be presented based on the imputations specified in Appendix III; Partial Date Conventions.

Definition of baseline values

The baseline value is defined to be the last value which was assessed before the 1st dose of study medication.

Clinical laboratory data on day 1 (Visit 1) will serve as baseline.

Baseline NRS will use the mean NRS score in the 7-days run-in period.

Baseline of 5D itch and Skindex-10 score will be assessed at Visit 1.

5.4 Multiple Comparison/Multiplicity

QMS Document Name: Statistical Analysis Plan	Page 12 of 33
QMS No (include version ref): STF-015-GL.02	Document date: 09JUL2019
CONFIDENTIAL	

No multiplicity adjustment is planned.

5.5 Covariates and Strata

In Mixed-effect model repeated measures analysis, baseline itch and prior anti-itch medication use will be considered as covariates for efficacy endpoints in Part B.

Strata is not applicable in this study.

6 Subject Accounting and Disposition

6.1 Subject accounting

The number and relative frequencies of subjects in each analysis set as defined in section 4 Analysis Sets will be presented overall and by randomised treatment .

Furthermore, the number and percentage of subjects in each analysis set will be presented overall and by treatment group including individual reasons of exclusion from the respective analysis set.

6.2 Disposition and withdrawals

A clear accounting of the disposition of all subjects who enter the study will be provided, from screening to study completion. The subject disposition summaries include a schematic diagram and a table with the registration status including the screening, randomization, discontinuation, and completion will be presented. The table will also include reasons of screen failure and discontinuation.

6.3 Protocol deviations

Protocol deviations will be presented in a listing including the date, severity, protocol deviation type, and the action taken, if any. The protocol deviation which impacts subject safety, ICH-GCP compliance, or efficacy endpoints could be marked as major protocol deviation per study team's approval prior to database lock.

- Any known study medication administration error with continuous 2 times (i.e. subject received incorrect IP dose)
- Any study specific related procedure done before the signature of the informed consent
- New clinical study procedures performed before participant was re-consented
- Missed safety or efficacy assessments related to primary or key secondary endpoints
- SAE(/pregnancy) reporting requirement not followed
- Identification or suspicion of activity which may be fraudulent
- Others will be identified by CP and Lumosa MM influencing Subjects' right and safety
- Source document/data missing
- Violation of inclusion/exclusion criteria

QMS Document Name: Statistical Analysis Plan	Page 13 of 33
QMS No (include version ref): STF-015-GL.02	Document date: 09JUL2019
CONFIDENTIAL	

- Subject who developed withdrawal criteria during the study but was not withdrawn
- Any significant non-compliance with persistent non-compliance with persistent non-compliance with persistent non-compliance to adhere to protocol and GCP requirements.

Protocol deviations will be summarized by treatment group. All subjects with protocol deviations including those specified above will be listed.

7 Demographics and Background Characteristics

7.1 Demographics

All demographics data will be performed based on data of Full Analysis Set. Demographics and baseline characteristics will be summarized using appropriate descriptive statistics.

Demographic characteristics will be summarized by overall subjects and treatment group, with corresponding listing as follows:

- Gender : Male, Female
- Age (years) : descriptive statistics
- Race : Asian, American Indian or Alaska Native, Black or African American, Native Hawaiian or Other, Pacific Islander, White, Other
- Weight (kg) at baseline : descriptive statistics
- Height (cm) at baseline : descriptive statistics
- BMI (kg/m²) at baseline : descriptive statistics

Body mass index (BMI) will be calculated automatically by the electronic data capture (EDC) system, using the following formula

$$\text{BMI (kg/m}^2\text{)} = \text{weight(kg) / height(m)}^2$$

Specifications for computation:

- Age (years): (date of given informed consent – date of birth + 1) / 365.25.
The integer part of the calculated age will be used for reporting purpose.

A demographic listing will be provided.

7.2 Disease characteristics

- Alcohol abuse history within 6 months: Yes, No
- Drug abuse history within 6 months: Yes, No
- Duration from the start of hemodialysis (months) : descriptive statistics

Duration from the start of hemodialysis (months) = [date of given informed consent – start date of hemodialysis) + 1] / 30.44
- Duration from the start of pruritus (months) : descriptive statistics

QMS Document Name: Statistical Analysis Plan	Page 14 of 33
QMS No (include version ref): STF-015-GL.02	Document date: 09JUL2019
CONFIDENTIAL	

Duration from the start of pruitus (months) = [date of given informed consent – start date of pruitus) + 1] / 30.44

For each of the above, if partial dates are recorded, the first day of the month will be imputed for missing day and January for missing month.

- Baseline anti-itch medications
- Baseline Worst Itching Intensity NRS
- Baseline 5D-itch scale total score
- Baseline Skindex-10 scale total score

